9.2 Sample Size Determination

Sample size calculations were performed for establishing evidence of a drug effect across the doses, that is, detecting a statistically significant dose response signal for the primary efficacy outcome in this study using the MCP-Mod approach.

Treatment effects are here presented on the log scale of average hourly counts, measured over 24 hours (see Section 9.4.2 for calculation details and interpretation).

Assuming a true change in cough count under placebo after 12 weeks of -0.19 (17% reduction), a maximum cough count change of -0.35 for BAY 1817080 over placebo (30%

reduction relative to placebo), a common standard deviation of 0.8, a set of plausible dose-response shapes including Emax and sigmoidal Emax models (chosen based on BAY 1817080 effects in Study 18184 combined with literature review), random allocation of participants to dose groups according to a 1:1:1:1 ratio, a sample size of 50 participants per dose groups will have at least 85% power to demonstrate a dose-response relationship, using a one-sided test at a type I error rate of $\alpha=0.10$. Approximately 236 participants will be randomized to achieve 200 evaluable participants for an estimated total of 50 evaluable participants per intervention group. The number of participants to be randomized might be increased if more participants than expected become unevaluable due to COVID-19 related circumstances, to maintain the goal of 50 evaluable participants per intervention group.

With this sample size, the dose-response curve is expected to be estimated with 80% confidence bands of half-widths of 0.14 to 0.16, depending on the underlying dose-response relationship.

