### 6.2.2.1 Secondary Efficacy Based on Cough Counts

- Percentage of participants with a  $\geq 30\%$  reduction from baseline in 24-hour cough count after 12 weeks of intervention

The proportion of participants meeting the responder threshold by intervention group will be compared across intervention groups using a Chi-square test.

Estimates and two-sided 80% and 95% confidence intervals will be provided for each treatment group and the treatment differences. Clopper Pearson confidence intervals will be calculated for each treatment group, while for treatment differences, due to the computational burden of exact unconditional confidence limits, Wald asymptotic confidence limits will be calculated.

The following two secondary efficacy endpoints will be analyzed with the same model as the primary efficacy endpoint.

- Change from baseline in 24-hour cough count after 2, 4, and 8 weeks of intervention.
- Change from baseline in awake cough frequency per hour after 2, 4, 8 and 12 weeks of intervention

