#### 6.2.4 Subgroup Analyses

The primary analysis of the primary and secondary endpoints will be repeated for the following subgroups:

- Duration of cough (since the start of Chronic Cough in years) (<10 years, ≥ 10 years)
- Baseline 24-hour coughs per hour
  - <10 coughs/hr, ≥10 coughs/hr
  - <20 coughs/hr, ≥20 coughs/hr
  - <30 coughs/hr, ≥30 coughs/hr
- Baseline awake coughs per hour (<20 coughs/hr, ≥20 coughs/hr)
- Baseline Cough Severity VAS (<60 mm, ≥60 mm)
- FEV1/FVC ratio (60 to <70, ≥70)
- Primary diagnosis: Unexplained Chronic Cough vs Refractory Chronic Cough
  - Patients with MHTERM = “Unexplained Chronic Cough” and MHOCCURN = “NO” will be assigned to the subgroup “Refractory Chronic Cough”.
  - Patients with MHTERM = “Unexplained Chronic Cough” and MHOCCURN = “YES” will be assigned to the subgroup “Unexplained Chronic Cough”.
- Standard Subgroups
  - Age (<60 years vs. ≥60 years; <65 years vs. ≥65 years)
  - Sex (male vs. female)
  - Race (white, black, Asian, other)
  - BMI (< 30 kg/m^2, ≥ 30 kg/m^2)
  - Weight (<60, 60 to <90, ≥90 kg)
  - Region:
    - Asia - Japan and Taiwan
    - Europe - Belgium, Czech Republic, France, Germany, Hungary, Italy, Netherlands, Poland, Slovakia, Spain, United Kingdom
    - Pacific - Australia
    - North America - United States and Canada
    - ROW - Argentina, Russian Federation, Turkey
- eGFR category at baseline (eGFR < 60 and ≥ 60 mL/min/1.73m^2)
- Smoking status:
  - Never

- Stopped smoking  $\geq 10$  years ago
- Stopped smoking 3 to  $< 10$  years ago
- Stopped smoking  $< 3$  years ago
  
- Background medication (medications taken at least once during the study):
  - azithromycin/erythromycin use the following ATC codes at the same time:
    - D06AX, D10AF, J01FA, S01AA (azithromycin)
    - D10AF, J01FA, S01AA (erythromycin)
  - gabapentin/pregabalin: use the following ATC codes at the same time
    - N02BG, N03AX, N07XX (gabapentin)
    - N02BG, N03AX, N05BX (pregabalin)
  - antihistamines with chronic cough indication: use the SDG "Antihistamines and antiallergics" and the indication
  - tricyclic antidepressants use all ATC codes for amitriptyline and amitriptyline hydrochloride at the same time (other tricyclic antidepressants are not relevant): G04BD, N02BG, N02CX, N05BX, N06AA
  - asthma medications: use the SDG "Drugs for obstructive airway diseases"
  - proton-pump inhibitors: use the SDG "Proton-pump inhibitors"

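### Responder-rate differences get Wald limits only because exact limits are slow; Miettinen-Nurminen score limits avoid that burden and hold 95% coverage better in small subgroups

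*SAP*

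**What the plan says.** For the responder endpoint based on cough counts, SAP 6.2.2.1 compares arms by a chi-square test and adds intervals: "Estimates and two-sided 80% and 95% confidence intervals will be provided for each treatment group and the treatment differences". Within each arm the method is exact: "Clopper Pearson confidence intervals will be calculated for each treatment group". For differences it is not: "for treatment differences, due to the computational burden of exact unconditional confidence limits, Wald asymptotic confidence limits will be calculated". Computing time is the only reason given, and score limits are not mentioned.

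SAP 6.2.4 then carries the analysis into subgroups: "The primary analysis of the primary and secondary endpoints will be repeated for the following subgroups". The list is long. Some levels look likely to be thin across four arms, such as a Pacific region made up of Australia alone. The section sets a floor of 5 participants, not stated as per arm, for the primary analysis and for the MMRM. It sets none for responder analyses.

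Protocol 9.2 plans on 50 evaluable participants per arm. Neither document states a responder rate, a subgroup size or a target coverage for these intervals.

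**The concern.** The choice is framed as exact unconditional limits or Wald limits, but there is a third family. Score limits are asymptotic, quick to compute and better behaved in small samples. The Newcombe form is closed; the Miettinen-Nurminen form needs a short iteration.

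The Wald interval takes its standard error from the observed proportions. An arm with no responders, or only responders, therefore contributes no variance. If both arms are like that, the interval shrinks to a point. In other small samples a limit can pass ±1, which no difference in proportions can reach. In a subgroup table the first case looks like certainty and the second is impossible. What is at stake is the reading of subgroup differences on one secondary endpoint.

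**Working it through.** **The plan's own figure.** Protocol 9.2 says that "a sample size of 50 participants per dose groups will have at least 85% power to demonstrate a dose-response relationship", with "a common standard deviation of 0.8" and a one-sided level of 0.10. A simulation of the maximum-contrast test (four candidate models, 196 degrees of freedom, critical value 1.485) gives power of 84.5%, 85.0%, 89.0% and 91.2%. The lowest is within simulation and rounding distance of 85%, so the planning values are read correctly. The documents give no coverage figure for the responder differences.

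**Responder rates implied by the planning values.** This is an assumption: the log change is taken as normal with SD 0.8 and means of -0.19 (placebo) and -0.54 (maximum). A 30% fall means a log ratio of at most ln 0.7 = -0.357.
- Placebo: Φ((-0.357 + 0.19)/0.8) = Φ(-0.21) = 0.417.
- Maximum effect: Φ((-0.357 + 0.54)/0.8) = Φ(0.23) = 0.59.

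Four further pairs were assumed to show a range: 0.5 vs 0.3, 0.6 vs 0.4, 0.4 vs 0.2 and 0.3 vs 0.1.

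**Formulas**, with d = p1 - p2 (observed) and N = n1 + n2:
- Wald: d ± z·√[p1(1-p1)/n1 + p2(1-p2)/n2].
- Miettinen-Nurminen: all values D for which (d - D)² ≤ z²·[q1(1-q1)/n1 + q2(1-q2)/n2]·N/(N-1), where q1 and q2 are the maximum-likelihood proportions under q1 - q2 = D.
- Coverage: the sum, over every pair of responder counts, of the two binomial probabilities multiplied together, counting only the pairs whose interval contains the true difference. This is full enumeration, not simulation.

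**Coverage of nominal 95% limits**

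| Per arm | Wald, 0.417 vs 0.59 | Wald, four assumed pairs | Miettinen-Nurminen, all five pairs |
|---|---|---|---|
| 50 | 94.4% | 94.2-94.5% | 94.8-95.3% |
| 10 | 92.9% | 92.2-93.9% | 95.6-96.7% |
| 5 | 88.8% | 81.0-89.2% | 93.7-98.5% |

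At 25 per arm, about half the trial, Wald covers 93.8% at 0.417 vs 0.59.

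**Nominal 80% limits.** Single rate pairs jump about at this level, so coverage was averaged over placebo rates of 0.35-0.50 and active rates of 0.45-0.70. Wald gives 79.1%, 76.6% and 72.5% at 50, 10 and 5 per arm. Miettinen-Nurminen gives 79.7%, 79.5% and 78.7%. The gain is not uniform: at 10 per arm, 0.5 vs 0.3 moves only from 75.1% to 75.2%, and 0.6 vs 0.4 from 74.5% to 74.6%.

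**Degenerate results at 95%**

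| Responders | Wald | Miettinen-Nurminen |
|---|---|---|
| 0/5 vs 0/5 | [0, 0] | [-0.46, 0.46] |
| 4/4 vs 0/4 | [1.00, 1.00] | [0.29, 1.00] |
| 3/5 vs 0/5 | [0.17, 1.03] | [0.001, 0.89] |

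At 5 per arm and 0.417 vs 0.59, 16% of Wald 95% intervals pass ±1.

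**Width.** At 0.417 vs 0.59 the mean 95% width, Wald against Miettinen-Nurminen, is 0.382 against 0.377 at 50 per arm, 0.817 against 0.780 at 10, and 1.079 against 1.021 at 5. At 0.3 vs 0.1 the order reverses: 0.632 against 0.693 at 10 per arm, and 0.801 against 0.971 at 5.

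**The case against.** The best defence is relevance. Wald is a standard, pre-specified interval, and at 50 per arm it loses about half a point. The endpoint is secondary and is compared by chi-square, so no error-rate claim rests on these limits. With 5 per arm no method gives a useful comparison, since 95% widths are close to 1 either way. All of that stands, and it is why the severity is low. It does not make Wald the better choice.

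Four stronger readings are tempting, and the documents do not support them.
- A reader might infer that subgroup limits are badly wrong throughout. At about 25 per arm the loss is only 1.2 points, and the SAP gives no sizes to show how many subgroups fall much below that.
- A reader might take arms with zero variance to be common. With 10 participants and a 10% rate the chance of no responders is 0.9¹⁰ = 35%. At 0.417 or 0.59 the chance of an all-or-none arm is about 0.5%. The 81% coverage figure likewise comes only from 0.3 vs 0.1; the other three assumed pairs give 87.2-89.2%.
- A reader might think that any closed-form score interval cures the problem. At 0.417 vs 0.59 and 5 per arm, Newcombe limits move coverage only from 88.8% to 89.6% at 95%, and from 72.1% to 72.3% at 80%.
- A reader might extend the point to every responder endpoint. SAP 6.2.2.3 and 6.2.3.1 describe intervals by group only for the VAS, LCQ and 50%/70% cough-count responders. That the differences are against placebo is also a reading, since SAP 6.2.2.1 does not say so.

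**Conclusion.** The point holds as a free improvement of low severity, limited to differences in the 30% cough-count responder rate. The reason the SAP gives for Wald limits does not exclude score limits. The shortfall at nominal 95% is about 0.5 point at 50 per arm, about 1 to 3 points at 10 per arm and about 6 to 14 points at 5 per arm. At the rates implied by the planning values it is 2.1 points at 10 per arm (95 - 92.9) and 6.2 points at 5 (95 - 88.8).

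The small-sample figures rest on assumed subgroup sizes and assumed responder rates, because the documents state neither. The zero-width and out-of-range limits follow from the Wald formula itself; only their frequency depends on those assumptions. The primary MCP-Mod result, the chi-square test and the sample size do not change.

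**What to change.** In SAP 6.2.2.1, replace the Wald limits for treatment differences by Miettinen-Nurminen score confidence limits, at both 80% and 95%, and state that this applies to the main and the subgroup analyses. Name this one method rather than a choice of methods, because it performs better than Newcombe in the thinnest groups.

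The cost is one phrase in the SAP and one program option. The limits are iterative rather than closed-form, and they are not symmetric about the estimate. When responder rates are low they are wider than Wald in small groups. At 80% with about 10 per arm, coverage stays near 75% for some rates, so the change does not fully repair that level.

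The sponsor could also state a minimum subgroup size for responder differences, since the floor in SAP 6.2.4 does not reach them. No interval method makes a comparison of 5 against 5 informative.

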### 6.2.2.2 HRQoL and PRO Associated Secondary Endpoints

- Change from baseline in cough related quality of life (measured by Leicester Cough Questionnaire (LCQ)) after 12 weeks of intervention.

The scoring algorithm described in the LCQ manual [9] will be used.

The analysis will be the change in LCQ (each domain as well as the total score) from baseline to week 12 using mixed model repeated measures (MMRM). This method will assume that any missing data is Missing at Random (MAR).

The model statement is:

$$\Delta Y_{jtkl} = Y_{j0} + \mu_0 + trt_k + visit_t + (trt * visit)_{kt} + region_l + P_j + \varepsilon_{jtkl},$$

where  $\Delta Y_{jtkl}$  is the change from baseline to visit  $t$  for subject  $j$  within treatment group  $k$  and region  $l$ .

- $\mu_0$  is the intercept
  - $Y_{j0}$  is the baseline covariate effect
  - $trt_k$  is the fixed effect of treatment group  $k$
  - $visit_t$  is the fixed effect visit  $t$
  - $(trt*visit)_{kt}$  is the interaction fixed effect of treatment  $k$  by visit  $t$
  - $Region_l$  is the fixed effect of stratification factor
  - $P_j$  is the patient specific random effect.
- $P$  and  $\varepsilon_{tkl}$  will be assumed as normally distributed random variables.

Correlations among measurements taken on the same patient will be modelled with an unstructured covariance assumption. The degrees of freedom will be computed according to the method detailed by Kenward and Roger.

For each active dose  $d_k$  the null hypothesis:

$$H_{0k}: \mu_1 = \mu_k$$

will be tested against the alternative hypothesis

$$H_{1k}: \mu_1 \neq \mu_k$$

within this model.

Least square mean estimates, estimates of treatment differences and corresponding confidence intervals (CIs) will be computed. The least square mean estimates of treatment difference at week 12 are the main estimates of interest; however, differences at all other visits and overall treatment differences (averaged across all visits) will also be estimated as exploratory endpoints.

The core SAS-code to be used is the following (variable and dataset names are for illustration only and may be subject to change):

```
proc mixed data=adqslcq;
  class subject treat visit region;
  model change = base treat visit region treat*visit /ddfm=KR;
  repeated visit / subject=subject type=un group=treat;
  lsmeans treat*visit /cl diff;
  ODS OUTPUT TESTS3=TYPE3 LSMMeans=LSMEAN ESTIMATES=ESTIM;
run;
```

If the model does not converge or the SAS log contains additional notes (e.g. that the Hessian matrix is non-positive definite), it will be tried to fit a simplified model assuming following covariance structure: without same covariate parameters within treatment groups (by deleting the group option) first, then heterogenous compound symmetry (CSH, without group option), then compound symmetry (CS, without group option).

- Change from baseline in cough severity after 12 weeks of intervention (measured by Cough Severity Visual Analogue Scale (VAS))

The change will be analyzed using MMRM as described above.

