#### **4.5.6 Unscheduled Visits and Safety Follow-up (SFU)**

Data from unscheduled visits will generally not be considered for descriptive tables with the exception of laboratory parameters see section 6.4.3 and 6.4.4. For the compliance calculation data from unscheduled visits will be used see section 6.4.2. The data from unscheduled visits will be displayed in the listings in Appendix 16 of CSR.

For cough severity VAS, PGI-S/C, EQ-5D-5L and LCQ, an extra line showing Safety follow-up (SFU) data will be added to the respective descriptive tables of the intervention period.

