#### 6.2.3.2 HRQoL and PRO Associated Exploratory Endpoints

- Change from baseline in cough severity after 2, 4, and 8 weeks of intervention (measured by Cough Severity VAS)

- Change from baseline in cough related quality of life after 2, 4, and 8 weeks of intervention (measured by LCQ) [each domain as well as the total score]

Summary statistics (arithmetic mean, SD, minimum, median, quartiles and maximum) and difference to baseline will be provided for the LCQ and VAS by treatment.

As exploratory endpoint the change in Cough Severity VAS and LCQ from baseline to Week 2, Week 4 and Week 8 will be analyzed with the same repeated measurement model as the secondary efficacy endpoint.

- Change from baseline in daily cough severity after 2, 4, 8, and 12 weeks of intervention (measured by the individual items of the Severity of Chronic Cough Diary [SCCD])
- Patient Global Impression of Change (PGI-C) and change from baseline in Patient Global Impression of Severity (PGI-S), after 2, 4, 8 and 12 weeks of intervention.

SCCD (individual items), PGI-C and PGI-S will be summarized by minimum, median, quartiles and maximum.

Frequency tables providing the number and percentages of the different response options to individual questions will be displayed for PGI-S and PGI-C.

In addition, changes from baseline for the single questions will be displayed.

These summary statistics and difference to baseline will be presented by treatment.

- Change from baseline in Health-related quality of Life (HrQoL) after 2, 4, 8 and 12 weeks of intervention (as measured by EQ-5D-5L)

Descriptive assessment will be done on the basis of the VAS and on dimension level assessment basis.

Frequency tables providing the number and percentages of the different response options to individual questions will be displayed. In addition, changes from baseline for the single questions will be displayed by treatment.

The EQ visual analogue scale (VAS) values of the EQ-5D-5L and their changes to baseline will be summarized by treatment as continuous variable; arithmetic mean, SD, minimum, quartiles, median and maximum will be displayed by treatment.

The scoring algorithm described in the EQ-5D-5L manual [11] will be used.

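### The LCQ and Cough Severity VAS repeated-measures model assumes one baseline slope for all four visits; if that slope changes over time, the Week 12 comparison may lose a little precision

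*SAP*

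**What the plan says.** SAP 6.2.2.2 writes the LCQ model with one baseline term, without a visit index, and says that it "is the baseline covariate effect". The code agrees: "model change = base treat visit region treat*visit /ddfm=KR". Treatment by visit is the only interaction. The residual covariance is unstructured and separate by arm: "repeated visit / subject=subject type=un group=treat". If the fit fails, only the covariance is simplified: the group option is dropped, "then heterogenous compound symmetry (CSH, without group option), then compound symmetry (CS, without group option". The mean model is the same at every step.

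For the VAS the section says: "The change will be analyzed using MMRM as described above". On the target of estimation it says: "The least square mean estimates of treatment difference at week 12 are the main estimates of interest".

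The model covers four post-baseline visits. SAP 6.2.3.2 states that change "from baseline to Week 2, Week 4 and Week 8 will be analyzed with the same repeated measurement model". Safety follow-up is not a fifth visit, because SAP 4.5.6 says only that "an extra line showing Safety follow-up (SFU) data will be added to the respective descriptive tables of the intervention period".

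**The concern.** In a repeated-measures model with a single baseline slope, every visit is adjusted with the same coefficient. That suits Week 12 only if baseline predicts Week 12 as it predicts Week 2. There are reasons to doubt it here. By SAP 4.5.5 the VAS baseline averages the 14 days up to Visit 2 and the Week 2 value averages 14 days up to that visit, so the two windows adjoin, while Week 12 lies ten weeks further on. The LCQ has a two-week recall (Protocol 8.1.2.4). Entry requires a VAS of at least 40 at screening (Protocol 5.1), which invites regression to the mean.

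The SAP also treats its endpoints differently. Cough counts at each visit use the primary ANCOVA (SAP 6.2.1.1 and 6.2.2.1), which has no visit term and is described as one model per time point, so each visit gets its own baseline slope. Only LCQ and VAS are held to a common one. At stake is the precision of the Week 12 LCQ and VAS differences from placebo. These are secondary results, and SAP 6.2.1.1 lists secondary variables among the inputs to the choice of target dose.

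**Working it through.** **The plan's own figures.** The documents state no SD, visit correlation, slope, effect or power for LCQ or VAS, so there is no figure to reproduce on this point. The nearest design figure is the primary-endpoint power in Protocol 9.2, and it reproduces. With SD 0.8, 50 per arm, one-sided alpha 0.10 and the four candidate models, the critical value is 1.475 and power is 84.7%, 85.2%, 89.2% and 91.4%, against a stated minimum of 85%. Also, 200/0.85 = 235.3, which rounds up to 236; the 15% is inferred. None of this uses the repeated-measures model.

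**Formula.** With complete data and a full treatment-by-visit mean model, the adjusted Week 12 difference is

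raw difference in change − b_c × (difference in mean baseline),

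where b_c = Σ w_t b_t is the common slope, b_t is the slope at visit t, and the weights w are proportional to Σ⁻¹1 for the residual covariance Σ of the four visits. A baseline-by-visit term replaces b_c with b_12. The variance ratio, common slope over visit-specific slope, is

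1 + (b_12 − b_c)² × Var(baseline) / residual variance at Week 12,

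and the SE ratio is its square root.

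**Worked example (correlations assumed).** Take all SDs as 1 and the correlation between two times as 0.5 + 0.4 × 0.3^(weeks apart/12): a stable patient level, a decaying part and 10% noise.

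- Correlations with baseline at Weeks 2, 4, 8, 12: 0.827, 0.768, 0.679, 0.620.
- Slopes of change on baseline (correlation − 1): −0.173, −0.232, −0.321, −0.380.
- Weights: 0.532, 0.209, 0.105, 0.155.
- b_c = −0.233, so b_12 − b_c = −0.380 + 0.233 = −0.147.
- Residual variance at Week 12: 1 − 0.620² = 0.6156.
- Variance ratio: 1 + 0.147²/0.6156 = 1.035. SE ratio: √1.035 = 1.017.

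**Range over assumed patterns.**

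| Pattern | Week 12 SE increase, constant SD | Same, SD rising from 1 to 1.3 |
|---|---|---|
| Equal correlation at all visits | 0% | 0.1% to 0.8% |
| Stable level + decay + noise (five settings) | 1.1% to 3.1% | 0.0% to 1.5% |
| Pure exponential decay, baseline to Week 12 correlation 0.3 to 0.8 | 3.4% to 8.6% | 0.0% to 5.9% |

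With constant SD, the weight of Week 12 in the common slope is 25% under equal correlation, 13% to 18% in the mixed patterns and 4% to 17% under pure decay. In those two decaying patterns Week 2 alone carries 51% to 96%. As an equivalent sample size, the mixed patterns with constant SD cost about 2% to 6%, and the whole range is about 0% to 18%.

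**Simulation check.** Four sets of 4,000 trials, 50 per arm, no true effect. The ratios of mean estimated SE were 0.998 (equal correlation 0.6), 1.015 and 1.029 (two mixed patterns) and 1.073 (pure decay, 0.5). Mean estimated differences were within 0.008 SD of zero under both models. The simulation pooled the covariance across arms and left out region and dropout.

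**The case against.** The strongest reply is that the loss is conditional and small. It arises only if the Week 12 slope differs from the pooled slope, and the documents cannot show that it does. Under equal correlation and constant SD the common slope is marginally better (0.998). If the SD rises while the correlation falls, the slopes can stay nearly equal. Participants have coughed for at least 12 months, and the VAS is averaged over 14 days; both favour stable patient levels. All of this stands, and it is why the point is minor.

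Cost is the second reply. SAP 6.2.4 runs the same model in subgroups of as few as 5 participants, that is 5 × 4 = 20 observations. The fixed effects there can already number 16 arm-by-visit means + 1 baseline + 2 region = 19, and three more make 22. This stands for those fits only, and they are fragile already.

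A reader might infer more than the documents support:

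- *That Week 12 is in fact adjusted with an early-visit slope.* Under equal correlation each visit weighs 25%, and no single early visit dominates.
- *That the treatment difference is biased.* Randomisation protects the complete-data comparison, and the simulation shows no bias. Bias under dropout would depend on a dropout pattern that the documents do not give.
- *That the LOCF rule, which SAP 6.2.2 extends to secondary endpoints, makes matters worse.* Carrying early values to Week 12 would, if anything, pull the Week 12 slope towards the earlier ones and shrink the gap.

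**Conclusion.** The point holds as a minor one. The LCQ and VAS model imposes a constant baseline slope without justification and departs from the per-visit adjustment used for cough counts. If the relation to baseline weakens over time, the Week 12 standard error is about 1% to 3% larger in the mixed patterns with constant SD and up to about 9% larger under pure correlation decay. It is not larger at all if the slope is constant. These figures rest on assumed correlations, complete data and a covariance pooled across arms. The primary MCP-Mod analysis and the sample size are untouched. A reader might infer that the dose choice is at risk, but SAP 6.2.1.1 rests that choice on primary, secondary and other efficacy variables together with safety, and nothing here shows that a change of this size would alter it.

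**What to change.** In SAP 6.2.2.2, give the baseline term in the equation a visit-specific coefficient, and append `base*visit` after `treat*visit` in the MODEL statement, leaving the Kenward-Roger option as it is. State that the term stays in the model at every covariance fallback, and that the change applies to LCQ and VAS alike. Otherwise, give a reason for the constant slope.

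The cost is three parameters with about 200 evaluable participants, in a model that already allows 10 × 4 = 40 covariance parameters, and no new data. If the slopes turn out equal, the loss is negligible (SE ratio 0.998). For the very small subgroups of SAP 6.2.4, the SAP can say in advance that the term is dropped if the model cannot be fitted.
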